### **2.6.10. CogState Computerized Cognitive Test Battery**

Cogstate is only applied to the subjects continued from Studies D1050301 and D1050326.

The CogState Computerized Cognitive Test Battery consists of 4 primary, individually administered tests in 4 distinct MATRICS cognitive domains, as detailed in Table 8.

Components of the CogState Computerized Cognitive Test Battery:

- Detection Task

In this task, subjects must respond to a card being displayed face up on the screen as quickly as possible. The score will be calculated as the mean of log10 transformed reaction times for correct responses. Lower scores indicate better performance.

- Identification Task

Subject must identify the color of a card as quickly as possible in this task. The score will be calculated as the mean of log10 transformed reaction times for correct responses. Lower scores indicate better performance.

- One Card Learning Task

In this task, subjects must remember which cards have been shown before in the task. The arcsine transformation of the square root of the proportion of correct responses will be recorded. Higher scores indicate better performance.

- One Back Task

In this task, subjects must

- (1) decide if each card is exactly the same as the previous card presented. The score will be calculated as the arcsine transformation of the square root of the proportion of correct responses. Higher scores indicate better performance.
- (2) identify the color of a card as quickly as possible in this task. The score will be calculated as the mean of log10 transformed reaction times for correct responses. Lower scores indicate better performance.

**Table 8      Cognitive Domains Evaluated in CogState Tests**

MATRICS Cognitive Domain	CogState Test	Data Type	Transformed Data from CogState
Psychomotor speed	Detection Task	Speed	Log10(S), S= reaction times for correct responses
Attention	Identification Task	Speed	Log10(S), S= reaction times for correct responses
Learning/Memory	One Card Learning Task	Accuracy	arcsine $\sqrt{R}$ , R=proportion of correct responses
Working Memory	One Back Task	Speed	Log10(S), S= reaction times for correct responses
		Accuracy	arcsine $\sqrt{R}$ , R=proportion of correct responses

A normative table of CogState Computerized Cognitive Test Battery for children and adolescent subjects is provided in [Attachment 4.2](#). For an individual domain, the age-specific standardized score for each task and data type is derived as below based on the subject's age (in years) at the study visit. The standardized scores are calculated by CogStat vendor (COGSTATE CT).

$$(\text{Score} - \mu_{age,domain}) \times \text{Multiplicand} / SD_{age,domain},$$

Where

$\mu_{age,domain}$  : mean of the norm group at the age (in years)

$SD_{age,domain}$  : standard deviation of the norm group at the age (in years)

Score : individual subject performance

Multiplicand: an indicator,

- Multiplicand = -1 when a lower score indicates improved performance (e.g. Detection task (speed), Identification task (speed), One Back Task (speed));
- Multiplicand = +1 when a higher score indicates improved performance (e.g. One Card Learning Task (accuracy), One Back Task (accuracy)).

Based on the standardized scores of individual task and data type (accuracy, speed) provided by the vendor, the sponsor will further derive the following composite scores for final analyses:

- (1) The standardized composite score is calculated as the mean of the standardized scores of Detection Task (speed), Identification Task (speed), One Back Task (speed), and One

Card Learning Task (accuracy). If two or more components are missing at a visit, the composite score will be set to missing.

(2) For each subject, change from baseline in standardized score for each of the 4 cognitive domains, and the standardized composite score will be derived at each assessed visit.

Definition of the standardized composite score in this SAP is same as the one in SAPs of interim analysis 1 and study D1050326 and is also same as the standardized composite score 2 in clinical study report of study D1050301.

### ***Analysis Methods***

#### **For subjects continued from Studies D1050301 and D1050326**

For CogState computerized cognitive composite standardized score and individual standardized domains scores, descriptive summaries (N, mean, standard deviation, median, and range) of observed and change from DB Baseline and OL Baseline will be provided by visit, W52 endpoint, and endpoint and analysis group and analysis subgroup, respectively.

#### **2.6.11. Columbia Suicide Severity Rating Scale (C-SSRS)**

C-SSRS is applied to the subjects continued from Study D1050301 and C-SSRS children version is applied to the subjects continued from Study D1050326. The C-SSRS Childrens' Version is distinguished from the adult version by the absence of questions regarding the duration, controllability, deterrents and reasons for ideation.

Severity of suicidal ideation is rated on a 6-point scale from 0='No ideation present' to 5='Active ideation with plan and intent'. A score of 4 or 5 on this scale indicates serious suicidal ideation. Suicidal ideation score is defined as the most severe suicidal ideation score (1-5 on the CSSRS) present at the assessment; assign a score of 0 if no ideation is present.

For subjects continued from study D 1050301, the ideation intensity total score is calculated as summation of the five items from the Ideation Intensity scale: frequency, duration, controllability, deterrents, and reasons for ideation. If one or more of these 5 items are missing at a visit, no imputation will be made and the corresponding ideation intensity total score will be set as missing. Items corresponding to frequency and duration are each rated on a scale from 1 to 5 and items corresponding to controllability, deterrents, and reasons for ideation are each rated on a scale from 0 to 5. If the patient did not endorse any suicidal ideation, set the intensity rating to 0. Thus, the possible range for the intensity total score is 0 to 25. For subjects continued from study D 1050326, the ideation intensity total score is not applicable and therefore will not be derived.

Suicidal behavior is collected as presence/absence of actual attempts, non-suicidal self-injurious behavior, interrupted attempts, aborted attempts, preparatory acts or behavior, and any suicidal behavior. In addition, the number of actual attempts, interrupted attempts, and aborted attempts are captured. Any attempt will be defined as suicidal behavior.

The lethality associated with actual attempts is rated on a 6-point scale from 0='No physical damage or very minor physical damage' to 5='Death'. Potential lethality of attempts is rated on a

3-point scale from 0='Behavior not likely to result in injury' to 2='Behavior likely to result in death despite available medical care'.

According to FDA draft guidance for suicidal ideation and behavior ([5], Appendix A), the following C-SSRS outcomes, which have binary responses (yes/no), are re-ordered and numbered to facilitate the further definitions of the composite endpoint and comparative endpoint of C-SSRS as below.

Category 1 – Wish to be Dead

Category 2 – Non-specific Active Suicidal Thoughts

Category 3 – Active Suicidal Ideation with Any Methods (Not Plan) without Intent to Act

Category 4 – Active Suicidal Ideation with Some Intent to Act, without Specific Plan

Category 5 – Active Suicidal Ideation with Specific Plan and Intent

Category 6 – Preparatory Acts or Behavior

Category 7 – Aborted Attempt

Category 8 – Interrupted Attempt

Category 9 – Actual Attempt

Category 10 – Completed Suicide

Category 11 – Self-injurious behavior without suicidal intent

Unless otherwise specified, C-SSRS table outputs will be presented by analysis subgroup for one analysis time point 'Any extension', whose definition is given in Table 9.

**Table 9 Analysis TimePoint for C-SSRS**

Analysis Timepoint	eCRF Visit(s) to be Involved	C-SSRS Version /Assessment Period	Derivation Rule
Any extension visit*	Up to EOT	Since last visit	Most severe value

\*: including all visits in open-label treatment period (see [Section 2.1.2](#)).

Comparative endpoints for 'Emergence' (outcomes that include events that first emerge) and 'Worsen' (outcomes that include events that worsen) will be derived below.

**Table 10.1 Comparative Endpoint Relative to DB Baseline**

Comparative Endpoints	Analysis Time Points Involved	Derivation Rule
Emergence of Suicidal Ideation	DB Baseline(a) Any extension visit(b)	No suicidal ideation at DB Baseline, and any type of suicidal ideation in 'any extension visit'
Emergence of Serious Suicidal Ideation		No suicidal ideation at DB Baseline, and any serious suicidal ideation [ideation score of 4 or 5] in 'any extension visit'

Emergence of Suicidal Behavior		No suicidal behavior at DB Baseline, and any type of suicidal behavior in 'any extension visit'	
Emergence of Suicidality		No suicidality at DB Baseline, and any suicidality in 'any extension visit'	
Worsening of Suicidal Ideation		Most severe suicidal ideation in 'any extension visit' is more severe than the most severe value at DB Baseline	
(a): Definition of DB Baseline: see Table 9 in D1050301 SAP, and Table 9 in D1050326 SAP ;			
(b): see Table 9.			

**Table 10.2 Comparative Endpoint Relative to DB Treatment Period**

Comparative Endpoints	Analysis Time Points Involved	Derivation Rule
Emergence of Suicidal Ideation	Any DB treatment period (a)	No suicidal ideation in DB treatment period, and any type of suicidal ideation in 'any extension visit'
Emergence of Serious Suicidal Ideation	Any extension visit (b)	No suicidal ideation in DB treatment period, and any serious suicidal ideation [ideation score of 4 or 5] in 'any extension visit'
Emergence of Suicidal Behavior		No suicidal behavior in DB treatment period, and any type of suicidal behavior in 'any extension visit'
Emergence of Suicidality		No suicidality in DB treatment period, and any suicidality in 'any extension visit'
Worsening of Suicidal Ideation		Most severe suicidal ideation in 'any extension visit' is more severe than the most severe value in any DB treatment period

(a): Definition of 'any DB treatment period': see 'any post-baseline' in Table 9 of D1050301 SAP, and 'any post-baseline' in Table 9 of D1050326 SAP ;  
 (b): see Table 9.

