### **1.2.1. Determination of Sample Size**

Subjects who complete the respective double-blind studies D1050301, D1050325 or D1050326, sign the consent, and meet all entry criteria are included in this study. Studies D1050301, D1050325, and D1050326 have finished, with a total of 271 subjects from D1050301, 125 subjects from D1050325, and 306 subjects from D1050326 enrolling into D1050302. Based on an estimated attrition rate of approximately 30% of subjects over six months, it is expected that at least 100 subjects are to be exposed to lurasidone for a minimum of 6 months for subjects continued from studies D1050301 and D1050325 in study D1050302.

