#### 2.1.5. Definition of Baseline Assessments

The following definitions will be used for effectiveness and safety assessments unless otherwise specified:

- **DB Baseline** (ie, Baseline assessment of the double-blind studies [D1050301, D1050325, or D1050326]): the last assessment made on or before the 1st dose of double-blind study medication as described in the SAPs of the core studies;
- **OL Baseline** (ie, Endpoint assessment of the double-blind studies [D1050301, D1050325, or D1050326] or Baseline assessment of the open-label study [D1050302]): the last assessment made on or before Day 1 of the extension study.

According to the protocol, measurement collected at OL Baseline is same as the value at visit 9 (ie, Week 6) (Study 301/325) or visit 8 (ie, Week 6) (study 326). For operation convenience, the protocol specified that data collected at the EOT visit of the core studies were to be recorded in core studies only and were not to be saved in the clinical database RAVE of the extension study. OL Baseline data in the Study Data Tabulation Model (SDTM) datasets of the study D1050302 will be obtained from corresponding core studies directly.

Unless otherwise specified, at each study visit of study D1050302, data derivation rule and missing imputation method for aggregated parameter that involves multiple individual items (eg, total score, subscale score, or composite score), are same as the corresponding ones in individual core study SAP. DB Baseline is defined same as the Baseline in individual core study per core study SAPs. DB Baseline used in the analysis of study D1050302 will be extracted from corresponding Analysis Data Set (ADS) of the core studies directly unless otherwise specified.

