### **2.1.9. Analysis Group and Analysis Subgroup**

A total of three analysis groups will be formed based on a subject’s previous participation of double-blind core studies. Column group “301/325/326” that combines these three analysis groups will be also presented. Summary tables will be labeled as follows:

- 301-Lur: Subjects continued from Study D1050301
- 325-Lur: Subjects continued from Study D1050325
- 326-Lur: Subjects continued from Study D1050326
- 301/325/326-Lur: All subjects combined

Subjects continued from Study D1050301 will be further grouped into 3 analysis subgroups (hereafter, referred as ‘Analysis Subgroup A’). Depending on the type of safety analysis in summary table they will be labeled as follows (ie, with 2 additional pooled groups: AllLur-Lur and 301-Lur):

- Pbo-Lur: previously randomized to placebo
- Lur40-Lur: previously randomized to lurasidone 40 mg/day
- Lur80-Lur: previously randomized to lurasidone 80 mg/day
- AllLur-Lur: previously randomized to lurasidone (40 mg/day or 80 mg/day)
- 301-Lur: subjects continued from study D1050301

Subjects continued from Study D1050325 will be further grouped into 3 analysis subgroups (hereafter, referred as ‘Analysis Subgroup B’). Depending on the type of safety analysis in summary table they will be labeled as follows (ie, with 2 additional pooled groups: AllLur-Lur and 325-Lur):

- Pbo-Lur: previously randomized to placebo
- Lur20-Lur: previously randomized to lurasidone 20 mg/day
- Lur60-Lur: previously randomized to lurasidone 60 mg/day
- AllLur-Lur: previously randomized to lurasidone (20 mg/day or 60 mg/day)
- 325-Lur: subjects from study D1050325

Subjects continued from Study D1050326 will be further grouped into 2 analysis subgroups (hereafter, referred as ‘Analysis Subgroup C’). Depending on the type of safety analysis in summary table they will be labeled as follows (ie, with one additional pooled groups: 326-Lur):

- Pbo-Lur: previously randomized to placebo
- Lur-Lur: previously randomized to lurasidone 20-80 mg/day
- 326-Lur: subjects from study D1050326

Subjects may be further grouped into 4 analysis subgroups based on the age at OL baseline (years) as needed (hereafter, referred as ‘Analysis Subgroup D’). Depending on the type of safety analysis in summary table they will be presented as follows (ie, with 2 additional pooled groups: 6-12 years old and  $\geq$  13 years old):

- 6-9 years old
- 10-12 years old

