### ***Analysis Methods***

#### **For subjects continued from Studies D1050301 and D1050326**

The number and percentage of subjects with following categories will be summarized by analysis group and analysis subgroup for any extension visit.

- each type of suicidal ideation,
- any suicidal ideation,
- each type of suicidal behavior,
- any suicidal behavior,

- any having self-injurious behavior without suicidal intent,
- any suicidality

In addition, for any extension visit, the number and percentage of subjects with following categories will be also summarized by analysis group and analysis subgroup.

- emergence of suicidal ideation,
- emergence of serious suicidal ideation,
- worsening of suicidal ideation,
- emergence of suicidal behavior,
- emergence of suicidality

Shifts from DB baseline and OL baseline to any post-OL baseline visit (ie, the worst case) in suicidal ideation score will be presented by analysis group and analysis subgroup, to show the percentage of subjects with values 0 ('No ideation present') to 5 ('Active ideation with plan and intent'). For subjects continued from study D1050301, ideation intensity total score will be provided in data listing. Data collected on actual suicide attempts (lethality of actual attempts and potential lethality of attempts) will be presented in a data listing.

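### SAP Table 10.2 counts emergence of serious suicidal ideation only in subjects with no ideation at all in double-blind treatment, so a first rise from score 1–3 to 4 or 5 is left out and no planned summary isolates it

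*SAP*

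**What the plan says.** SAP 2.6.11 scores ideation from 0 (none) to 5 and sets the threshold for seriousness: "A score of 4 or 5 on this scale indicates serious suicidal ideation". The text after Table 9 describes emergence endpoints as "outcomes that include events that first emerge".

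Table 10.2 takes the DB treatment period as its reference. Its serious-ideation row reads "No suicidal ideation in DB treatment period, and any serious suicidal ideation [ideation score of 4 or 5". Table 10.1 takes DB baseline as its reference, with the same structure: "No suicidal ideation at DB Baseline, and any serious suicidal ideation [ideation score of 4 or 5". In both tables, worsening of ideation is any extension worst score above the reference.

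The Analysis Methods of SAP 2.6.11 plan counts at any extension visit of each ideation type, any ideation, and the emergence and worsening endpoints. They also plan "Shifts from DB baseline and OL baseline to any post-OL baseline visit (ie, the worst case) in suicidal ideation score", shown on the 0–5 scale. No shift from the worst DB-treatment score is planned. OL baseline is defined in SAP 2.1.5 as "the last assessment made on or before Day 1 of the extension study", which is a single assessment and not a worst value over the DB period.

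**The concern.** The label of the row is wider than its rule. A reader who sees a count for emergence of serious ideation, in a document that defines serious as 4 or 5 and emergence as first occurrence, will tend to read it as all new-onset serious ideation. It is the part of that group that came from no ideation at all.

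The other emergence rows of Table 10.2 match reference and event at the same level: no ideation then ideation, no behavior then behavior, no suicidality then suicidality. Only the serious-ideation row has a broader exclusion at the reference than its event.

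Safety is part of the primary objective, and Protocol 11.1.2 ties Type 4 and Type 5 ideation to discontinuation, so this is a row that will be read closely. The omitted group need not be empty. The only suicide-related exclusion in Protocol 8.2 is imminent risk in the investigator's judgment, so DB-treatment scores of 1–3 do not by themselves prevent entry.

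**Working it through.** No sample size, power or test is involved. The check applies the printed rules to the possible scores.

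Inputs: the 0–5 scale and the threshold of 4 (SAP 2.6.11), the Table 10.2 rules, the planned outputs (SAP 2.6.11, Analysis Methods) and the group sizes (SAP 1.2.1).

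**Step 1. What Table 10.2 counts.**

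| Worst DB-treatment score | Worst extension score | First reach of 4–5? | Serious-emergence row | Worsening row |
|---|---|---|---|---|
| 0 | 4 or 5 | yes | counted | counted |
| 1, 2 or 3 | 4 or 5 | yes | **not counted** | counted |
| 4 | 5 | no | not counted | counted |
| 4 or 5 | 4 or 5, no increase | no | not counted | not counted |
| 0, 1 or 2 | higher, but at most 3 | no | not counted | counted |

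The row is a subset of the new-onset group, so it can equal that group or fall short of it, but cannot exceed it.

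**Step 2. Whether another planned output isolates the second line.**

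- *Worsening* includes it, together with increases such as 0 to 1 and 4 to 5.
- *Counts of each ideation type at any extension visit* include it but ignore DB history.
- *Shift from DB baseline* shows the 1–3 to 4–5 cells. This fills the gap for Table 10.1, but not for Table 10.2.
- *Shift from OL baseline* starts from one assessment.

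Two subjects show that the gap is real. Suppose both have DB baseline 0, OL baseline 0 and the same extension assessments, with a worst score of 5. Subject A had a worst DB-treatment score of 2, and subject B of 4. Against Table 10.1 both are emergent, seriously emergent and worsened. Against Table 10.2 neither is emergent or seriously emergent, and both are worsened (5 > 2 and 5 > 4). Both sit in the 0-to-5 cell of both shift tables. Their entries agree in every planned C-SSRS summary, yet only A is new onset relative to DB treatment.

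**Step 3. What the OL-baseline shift can say.** Its 0–3 to 4–5 cells take in the new-onset subjects and also anyone, like B, who had already scored 4 or 5 in DB treatment. Their sum is an upper bound on the new-onset count only if three conditions hold:

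1. OL baseline is present for every such subject. SAP 2.1.14.1 does not impute a missing one, and a subject without it has no starting row.
2. The Week 6 core visit that supplies OL baseline belongs to the DB-treatment reference. That definition is in Table 9 of each core SAP, which the documents cite but do not reproduce. If Week 6 lies outside it, a subject with worst DB score 2 and OL baseline 4 could be new onset yet fall outside the 0–3 starting rows.
3. Extension visits mean the same in both outputs. Under SAP 2.1.2 and the Table 9 footnote, any extension visit includes the OL Baseline visit for subjects previously on lurasidone. The shift uses post-OL-baseline visits only.

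**Step 4. Size per subject.** SAP 1.2.1 gives the groups: "with a total of 271 subjects from D1050301, 125 subjects from D1050325, and 306 subjects from D1050326 enrolling into D1050302". C-SSRS is applied to D1050301 and D1050326 only. If all enrolled subjects were dosed:

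- 1/271 = 0.37%
- 1/306 = 0.33%

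The comparative endpoints are also reported by analysis subgroup. For instance, "Subjects continued from Study D1050301 will be further grouped into 3 analysis subgroups". One subject weighs more there, but the subgroup sizes are not given.

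**The case against.** The strongest reply is that this is a preference and not an error. The rule is printed beside the label, so the endpoint is fully specified. The SAP can be read as separating emergence, which starts from nothing, from worsening, which is any increase; a move from 2 to 5 is then worsening by design. Nor is the SAP uniform elsewhere: UKU Table 11.2 matches levels for drug-related emergence, while UKU Table 11.1 does not. The study is descriptive and tests nothing (SAP 2.2.1).

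Much of this stands. The row is not ambiguous, and the SAP does not contradict itself in a way that prevents programming. What does not stand is the suggestion that existing outputs make the missing figure available, as subjects A and B show.

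A reader might infer that cases of serious ideation go unreported. The documents do not support that. Every subject with Type 4 or 5 ideation at an extension visit is in the type counts, and suicidality and self-injury adverse events are summarised separately (SAP 2.6.4). What is lost is a classification, not the event.

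A reader might also infer that the OL-baseline shift supplies the missing number or always caps it. It does neither without the conditions in step 3.

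It can also be argued that, if the core studies removed every subject with Type 4 or 5 ideation, no entrant would have had such a score in DB treatment, and subtracting the current row from all subjects with 4 or 5 in the extension would give the omitted number. That may be so, but the core-study rules are not in the documents, and no planned row would report the result.

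**Conclusion.** The point holds as a cheap improvement that should be made. The serious-emergence row of Table 10.2 omits first moves from 1–3 to 4 or 5, its label does not say so, and no planned summary isolates those subjects against the DB-treatment reference. Table 10.1 shares the rule but not the gap.

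The direction is certain: the row is at or below the true new-onset count. The size is not known. The documents give no ideation frequencies, so the number omitted may be zero, and a claim that the reported figure is materially too low would go beyond them. The per-subject percentages rest on all enrolled subjects having been dosed. The OL-baseline shift is an approximate view only.

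**What to change.** Add to Table 10.2 a row defined as no serious suicidal ideation (score 0–3) in the DB treatment period, and score 4 or 5 at any extension visit. Keep the current row, relabelled as emergence of serious suicidal ideation from no ideation, with a footnote giving the present label. The same row may be added to Table 10.1 for consistency, although it would partly duplicate the DB-baseline shift table.

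The cost is one row and a footnoted relabel, from values already derived. The new count will equal or exceed the current one, and the footnote should say so. According to SAP section 1, the schizophrenia study report and both interim analyses are already done, so for the D1050301 subjects the new row would first appear in the full study report. Keeping the current row preserves comparability with that earlier report, and with the interim reports if their separate plans, which are not in the documents, used the same rule.
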